12.1.6 Phase II Sample Size Justification (Cohort A and Cohort B)

Let π equal the proportion of CR+PR responses. The primary analysis, for Cohort A and Cohort B, will consist of a one-sided exact binomial test of H₀: π =0.05 versus H_a: π >0.05 at level α =0.05. Given n=18 subjects and setting power at 0.80 we will be able to detect an alternative response rate of π >0.29. The primary analysis for Cohort B will consist of a one-sided exact binomial test of H0: π =0.30 versus Ha: π >0.30 at level α =0.05. Given n=39 subjects (including n=6 from the Phase I) and setting power at 0.80 we will be able to detect an alternative response rate of $\pi > 0.50$. A secondary analysis of efficacy will utilize an ordinal regression of response (CR, PR, SD, PD) as a function of baseline tumor volume. All key secondary outcomes will be considered suitably continuous will be analyzed with an analysis-of-covariance (ANCOVA) approach regressing change from baseline to three months on the baseline value of the respective measure adjusted for baseline tumor volume, age, and sex. The null hypothesis of interest is H₀: $\beta_0=0,\beta_1=0$ versus H_a: $\beta_0 \neq 0, \beta_1 \neq 0$, where β_0 is the ANCOVA intercept and β_1 is the regression slope, respectively. All tests will be at level α =0.05. Since both the FACT-L based measures and the 6-minute walk measures are likely to be highly cross correlated no adjustments for multiple testing will be considered a priori. For Cohort A and Cohort B, each continuous endpoint and given n=18 subjects we will have 0.80 power to reject the joint null hypothesis if the slope and intercept account for 39% of the overall variation or larger in the given endpoint. For Cohort B, each continuous endpoint and given n=39 subjects we will have 0.80 power to reject the joint null hypothesis if the slope and intercept account for 20% of the overall variation or larger in the given endpoint.

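### The 0.80 power claimed for the FACT-L and walk-test ANCOVAs is about 0.77 for Cohort B (n=39, 20% of variation); the n=18 figure (39%) holds only if the planned covariates are left out of the model

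*Combined protocol and SAP*

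**What the plan says.** Section 12.1.6 plans an ANCOVA for the FACT-L and 6-minute-walk measures. Change from baseline to three months is regressed "on the baseline value of the respective measure adjusted for baseline tumor volume, age, and sex". The null hypothesis sets two coefficients to zero together: β_0 "is the ANCOVA intercept and β_1 is the regression slope, respectively". On error rates the section says "All tests will be at level α =0.05" and, for these measures, that "no adjustments for multiple testing will be considered a priori".

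Two power statements follow, each at 0.80:

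- with n=18, "if the slope and intercept account for 39% of the overall variation or larger in the given endpoint";
- for Cohort B, with n=39, "if the slope and intercept account for 20% of the overall variation or larger in the given endpoint".

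The section does not give the formula, the residual degrees of freedom or the noncentrality. It also does not say whether the share is a partial one or a share of total variation.

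**The concern.** The two statements fix everything a standard calculation needs except the residual degrees of freedom and the noncentrality convention, so they can be checked. The n=39 figure comes out short under each convention tried. The n=18 figure matches only a two-parameter model, whereas the plan specifies five parameters.

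What is at stake is limited but real. Section 12.1.6 is where the plan states a detectable effect for these endpoints, and section 12.1.4 says the data will inform a randomized Phase IIb trial. A reader who relies on 12.1.6 would take the detectable effect to be slightly smaller than it is.

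**Working it through.** **Inputs, all from section 12.1.6.** Level α = 0.05. Numerator degrees of freedom u = 2 (intercept and baseline slope tested together). n = 18 with R² = 0.39, and n = 39 with R² = 0.20. Target power 0.80. The planned model has an intercept, the baseline value, tumor volume, age and sex. That is 5 parameters, so residual degrees of freedom v = n − 5 (13 or 34). Without the three covariates, v = n − 2 (16 or 37).

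**Formulae.** Effect size f² = R²/(1 − R²). Power = P[F′(u, v, λ) > F₀.₉₅(u, v)], where F′ is noncentral F. Two conventions for λ are in use: λ = n·f², and Cohen's λ = (u + v + 1)·f².

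**Effect sizes.**
- n=18: f² = 0.39/0.61 = 0.639.
- n=39: f² = 0.20/0.80 = 0.25.

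**Step 1. Reproduce the plan's figures with no covariates (v = n − 2).**

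| n, share | λ convention | λ | Power | Minimum share for 0.80 |
|---|---|---|---|---|
| 18, 39% | n·f² | 18 × 0.639 = 11.51 | 0.793 | 39.4% |
| 18, 39% | Cohen | 19 × 0.639 = 12.15 | 0.816 | 38.1% |
| 39, 20% | n·f² | 39 × 0.25 = 9.75 | 0.770 | 21.2% |
| 39, 20% | Cohen | 40 × 0.25 = 10.00 | 0.781 | 20.7% |

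The n=18 figure reproduces: with λ = n·f², the minimum share of 39.4% rounds to the printed 39%. The same convention gives 21%, not 20%, at n=39. Cohen's λ comes closest at n=39, but it uses a multiplier of 40 for 39 patients and still gives 0.781, with a minimum share that rounds to 21%.

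**Step 2. Use the planned model (v = n − 5), with the covariates explaining nothing further.**

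| n, share | λ convention | λ | Power | Minimum share for 0.80 |
|---|---|---|---|---|
| 18, 39% | n·f² | 11.51 | 0.774 | 40.5% |
| 18, 39% | Cohen | 16 × 0.639 = 10.23 | 0.721 | 43.4% |
| 39, 20% | n·f² | 9.75 | 0.767 | 21.3% |
| 39, 20% | Cohen | 37 × 0.25 = 9.25 | 0.743 | 22.2% |

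With λ = n·f², charging the three covariates costs 0.793 − 0.774 = 0.019 at n=18 and 0.770 − 0.767 = 0.003 at n=39. The n=39 shortfall is therefore mostly not a covariate effect.

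**Step 3. How much covariate explanation would restore 0.80?** Suppose the printed share is of total variation and the covariates explain a further share c. Then λ = n·R²/(1 − R² − c), with v = n − 5. Solving for power 0.80:
- n=18: c = 0.037, λ = 18 × 0.39/(0.61 − 0.037) ≈ 12.25.
- n=39: c = 0.060, λ = 39 × 0.20/(0.80 − 0.060) ≈ 10.54.

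With c = 0.10, power would be 0.846 (n=18) and 0.823 (n=39).

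**The case against.** The strongest case against acting has three parts.

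**The n=18 figure is right on a simple reading.** This stands. A reader might infer that both printed figures are wrong outright. The documents do not support that: a two-parameter model gives 39.4%, which rounds to 39%, and Cohen's λ gives power above 0.80. The n=18 figure falls short only when the planned covariates are charged.

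**Charging covariates while giving them no explained variation is one-sided.** This stands in part. The plan's wording about overall variation can be read as a share of the total, and modest prognostic value in tumor volume, age and sex would bring the adjusted model to 0.80 or above. But section 12.1.6 neither assumes nor mentions such value. A power statement that depends on it should say so. Without it, neither λ convention reaches 0.80 at n=39 and 20%.

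**Nothing depends on these figures.** This largely stands. A reader might infer that the trial is under-sized, or that a primary analysis lacks its planned power. Section 12.1.6 ties n=18 and n=39 to the exact binomial test of response, which this point does not touch, and no decision rule uses the ANCOVA power. The standing of the endpoints is also unsettled in the documents. Section 4.1.2 and the opening of section 12 list them as primary, section 12.1.3 calls them additional, and section 12.1.6 introduces the same ANCOVA under key secondary outcomes.

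**Conclusion.** The point holds, at minor weight. For Cohort B the printed 0.80 at 20% is not delivered: power is about 0.77 and the share needed is about 21% (20.7% to 22.2% across the conventions tried). For n=18, the printed 39% is sound for a model without covariates. For the ANCOVA that the plan specifies, power is about 0.77 and the share needed is about 40.5% (43.4% with Cohen's λ).

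The main shortfall is about 3 points of power (0.80 − 0.774 = 0.026 and 0.80 − 0.767 = 0.033). With Cohen's λ and the covariates charged it reaches 7.9 points at n=18 and 5.7 at n=39.

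The adjusted-model results assume that the covariates explain no further variation. All the results assume, as the plan's own figures do, that every one of the 18 or 39 patients contributes a three-month value.

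**What to change.** In section 12.1.6:

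- restate the Cohort B figure as 0.80 power at about 21% of variation, or about 0.77 power at 20%;
- restate the n=18 figure as 0.80 power at about 40–41%, or about 0.77 power at 39%;
- say that residual degrees of freedom are n − 5, to match the planned covariates;
- name the noncentrality used, and say whether the share is partial or of total variation. If the covariates are expected to explain variation, give the assumed amount.

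The cost is two numbers and a sentence or two, and a slightly less favorable detectable effect. The sample size, the analysis and the conduct of the trial stay as they are.

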12.1.7 Interim Analysis and Criteria for Early Termination of the Study

A futility analysis of efficacy will be carried out for Cohort B after n=20 subjects have completed the trial. A conditional power calculation will inform the decision to continue accrual.

12.1.8 Safety Monitoring (Cohort A and Cohort B)

Safety and tolerability will be assessed by incidence, severity, and changes from baseline of all relevant parameters including adverse events (AEs), laboratory values and vital signs.

Vital sign results (systolic and diastolic blood pressure, pulse, respiration, and temperature) will be summarized descriptively for each scheduled and unscheduled protocol time point. Changes will be calculated relative to the assessments at baseline.

The changes in hematology, chemistry, and other laboratory values will be summarized descriptively for each scheduled and unscheduled protocol assessment time point. Changes will be calculated relative to the values collected at baseline. Data listings of all laboratory data collected during the study will be presented. Laboratory values outside normal limits will be identified in data listings and will include flags for high and low values.

The frequency of toxicities will be tabulated by grade. All participants who receive any study treatment will be considered evaluable for toxicity.

12.1.9 Safety Monitoring Lead-In (Cohort B)

The safety profile will be measured by recording treatment related AEs that are \geq grade 4 with attribution of 'possible', 'probable', or 'definite', according to the NCI CTCAE v5.0. The safety measures will be evaluated in all patients who received image-guided I-PDT preceded by standard of care p-XRT of 8 Gy x1 for the treating their MCAO. The following decision rules will be followed: (i) If 0/3 AE \geq grade 4's are observed it will be concluded the therapy is safe. (ii) If 1/3 AE \geq grade 4's are observed, enroll 3 more patients for safety evaluation. If 1/6 AE \geq grade 4's are observed it will be concluded the therapy is safe. If \geq 2/6 AE \geq grade 4's are observed it will be concluded that therapy is unsafe. We calculated via Monte Carlo simulation that if the AE \geq grade 4 rate is 20%, 30% and 40% the respective probabilities of declaring the treatment unsafe are 0.26, 0.51 and 0.70.

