4 METHODOLOGY

4.1 Study Design

This is a multi-center, multi-arm, Phase I (Cohort 0; data collection complete) to monitor the safety and Phase II study (Cohort A and Cohort B described below) to monitor the efficacy of EBUS-

TBN guided I-PDT and/or I-PDT and/or PDT in patients with malignant airway obstructions that are refractory to curative chemoradiation or, who are not candidates for curative chemoradiation. Participants will be treated on an outpatient or inpatient basis, and the treating physician will make this decision on a case-by-case basis.

Cohort 0 is closed to accrual and fulfilled the Phase 1 safety monitoring requirements. Cohort 0 provided the safety monitoring component for Cohort A of this Phase II study. Cohort 0 consisted of patients with the diagnosis of lung cancer that received porfimer sodium with EBUS I-PDT and participated in all of the study procedures except the Quality of Life Questionnaires and Six Minute Walk Test.

Cohort A (n=18, Phase II) consists of patients with a diagnosis of lung cancer or other malignancies causing airway obstruction or inoperable malignancies not candidates for curative radiotherapy within the airway; and that receive EBUS I-PDT and all of the study procedures. Subjects treated in Cohort 0 are considered the Phase I part of Cohort A.

Cohort B (n=39) will consist of patients with the diagnosis of lung cancer or other malignancies causing airway obstruction, or inoperable malignancies not candidates for curative radiotherapy within the airway. Subjects in Cohort B will receive the EBUS-guided I-PDT 48 ± 4 h after standard of care palliative radiotherapy of 8 Gy x1.

NOTE: Given the nature of this advanced airway procedure, only the physician performing the procedure will be the consenter for the procedure as well as for the study.

All participants will undergo the standard of care interventional bronchoscopy procedure with an attempt to treat and resolve the airway obstruction using conventional methods such as mechanical debulking, tumor ablation, and/or airway stenting. Airway stenting will be performed before or after I-PDT and/or PDT, as necessary. Curvilinear EBUS with Color Doppler will be used to guide the intra-tumor fiber insertion.

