4.1.4 Target Accrual and Study Duration

Eight patients in the Phase I (Cohort 0), and 18 patients will be enrolled in the Phase II Cohort A (8 already enrolled under Phase 1 portion of Cohort A from previous protocol version) and 39 in Cohort B (65 patients total). It is expected to have up to 32 patients enrolled from accompanying external sites and the remainder enrolled from Roswell Park. Accrual is expected to take up to 10 years.

Patients will be drawn from the interventional pulmonology practice and from referrals from medical oncologists. All patients will come off study at 24 weeks.

Enrolled patients who do not receive the I-PDT and/or PDT for any reason (such as patient withdrawal, safety or inability to deliver the I-PDT) will be replaced.

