8.1.3 Days Prior to the EBUS Guided I-PDT Procedure

- All participants will have a blood draw for CBC with automated differentials and CMP within 2 days prior to administration of porfimer sodium. Additionally, patients on chemotherapy will have a blood draw within 2 days for CBC and CMP prior to PDT.
- For all participants: systemic administration of 2 mg/kg porfimer sodium 48 ± 4 hours (Day -2) prior to I-PDT as described in Section 6.1.1.
 - Blood draw for immune biomarkers prior to the administration of the porfimer sodium.
 - For Cohort B participants only: standard of care palliative radiotherapy of 8 Gyx1 will be administered to the target tumor at day -2 just before systemic administration of 2 mg/kg porfimer sodium. This will be coordinated with the radiation oncologist.

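### In the Cohort B safety lead-in, a related grade 4 or higher event that prevents I-PDT falls outside the decision rule

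*Combined protocol and SAP*

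**What the plan says.** Four parts of the combined protocol and SAP bear on this.

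- **Lead-in population (12.1.9).** "The safety measures will be evaluated in all patients who received image-guided I-PDT preceded by" palliative radiotherapy. The counted event is a treatment-related adverse event of grade 4 or higher, "with attribution of 'possible', 'probable', or 'definite', according to the NCI CTCAE v5.0". With 0 of 3 the therapy is declared safe. With 1 of 3, three more patients are enrolled; 1 of 6 is then safe, and 2 or more of 6 is unsafe.
- **Replacement (4.1.4).** The rule covers "Enrolled patients who do not receive the I-PDT and/or PDT for any reason", with examples: "such as patient withdrawal, safety or inability to deliver the I-PDT) will be replaced". It makes no exception for the lead-in.
- **Timing (4.1 and 8.1.3).** "Subjects in Cohort B will receive the EBUS-guided I-PDT 48 ± 4 h after standard of care palliative radiotherapy of 8 Gy x1". The radiotherapy "will be administered to the target tumor at day -2 just before systemic administration of 2 mg/kg porfimer sodium". Both are therefore given about two days before light.
- **General safety reporting (12.1.8).** After stating that toxicities are tabulated by grade, the section adds: "All participants who receive any study treatment will be considered evaluable for toxicity".

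Section 12.1.9 does not say whether the event of a replaced patient counts in the lead-in.

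**The concern.** The lead-in decides whether the Cohort B regimen goes forward, and it does so on three or six patients. Its population is fixed by something that happens after treatment has begun, namely receipt of light. A patient who has had radiotherapy and porfimer sodium, then has a related grade 4 or 5 event and is not illuminated, leaves the denominator and is replaced by someone who does reach light.

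The route is plausible. Light delivery requires bronchoscopy under general anesthesia (6.1.2), a pre-operative examination is required on Day 0 (8.1.4), and a patient not cleared by the anesthesiologist is excluded (5.2). A patient who dies before Day 0 cannot be illuminated at all. The most severe pre-light events are thus the ones most likely to be missed. With only three patients, one uncounted event changes the decision from expand to declare safe.

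**Working it through.** **Inputs.** The decision rule and the stated operating characteristics come from 12.1.9, the replacement rule from 4.1.4, and the timing from 4.1 and 8.1.3. Section 12.1.9 does not state the outcome for 2 or 3 events in the first 3 patients; I take it as unsafe.

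**Step 1: the plan's own figures.** Let p be the probability of a related grade 4 or higher event in a counted patient. The regimen is declared safe with 0 of 3, or with 1 of 3 followed by 0 of the next 3:

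P(unsafe) = 1 − [(1−p)³ + 3p(1−p)⁵]

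- p = 0.20: 1 − (0.512 + 0.197) = 0.291 (stated 0.26)
- p = 0.30: 1 − (0.343 + 0.151) = 0.506 (stated 0.51)
- p = 0.40: 1 − (0.216 + 0.093) = 0.691 (stated 0.70)

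A simulation of one million runs agrees with the exact values. The 30% and 40% figures match to within 0.01. The 20% figure is 0.03 too low. That is a separate matter and does not affect this point.

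**Step 2: the rate the rule sees.** Let p now be the event rate in all patients who start the regimen. Let s be the share of those events that occur before light and prevent it. Patients with such events are replaced, so the rate among patients who reach light is

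r = p(1−s) / (1−ps)

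Patients who miss light without an event are assumed to be replaced by patients with the same risk, so they do not alter r.

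Example with p = 0.30 and s = 0.25: r = 0.225/0.925 = 0.243, and P(unsafe) = 1 − (0.757³ + 3 × 0.243 × 0.757⁵) = 0.386.

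**Step 3: range over s.** The documents give no value for s, so it is an assumption throughout.

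| Share s | r at p = 20% / 30% / 40% | P(unsafe) at p = 20% / 30% / 40% |
|---|---|---|
| 0 | 0.200 / 0.300 / 0.400 | 0.291 / 0.506 / 0.691 |
| 10% | 0.184 / 0.278 / 0.375 | 0.256 / 0.461 / 0.649 |
| 25% | 0.158 / 0.243 / 0.333 | 0.202 / 0.386 / 0.572 |
| 50% | 0.111 / 0.176 / 0.250 | 0.113 / 0.241 / 0.400 |

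The loss in P(unsafe) is about 0.04 at a 10% share, 0.09 to 0.12 at 25%, and 0.18 to 0.29 at 50%. At 5% and a true rate of 30%, P(unsafe) is 0.484, a loss of about 0.02.

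The operating characteristics in 12.1.9 therefore describe the whole regimen only if s is zero. Otherwise they describe the event rate among patients who reached light.

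**The case against.** The best defense is that the lead-in population matches the question asked. Section 6.1.10 says the unknown risk is that of giving I-PDT two days after palliative radiotherapy. The protocol treats the radiotherapy as standard of care and describes the porfimer sodium dosing as clinically approved. A set of patients who received the full sequence answers that question. This stands to a point: a reader might infer that the protocol calls the risk of radiotherapy plus drug unknown, and it does not. But the rule is used to declare the therapy safe, and the therapy begins on Day -2.

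Second, the events are not lost to oversight. Serious events are reportable from consent and within 24 hours of awareness (10.1.5), unanticipated problems within one business day (10.1.7), and the institution may stop the study at once for safety (15.1.2). All this stands. None of it feeds a replaced patient's event into the lead-in count, and the stated DSMC review is annual (section 11).

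Third, 12.1.8 might be read as contradicting 12.1.9, or as already solving the problem. Neither reading is secure. The 12.1.8 sentence belongs to the toxicity tabulation, while 12.1.9 sets its own population for one decision. Nor does 12.1.8 say that radiotherapy is study treatment; the table in section 6 lists it as an additional therapy.

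Fourth, the pre-light window is only about 48 hours, whereas adverse events are collected to 30 days after the last intervention (10.1.3). The procedural risks in 6.1.10, such as bleeding and airway perforation, arise on or after Day 0. The share may well be small, which is why the table includes 10% and the text 5%.

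**Conclusion.** The point holds in limited form. Followed as written, 12.1.9 and 4.1.4 together leave out of the lead-in rule any related grade 4 or higher event that occurs after radiotherapy or porfimer sodium and prevents light delivery. The gap in the text does not depend on any assumed figure. Its numerical effect does: negligible if almost no events fall in that class, about 4 points of P(unsafe) at a 10% share, 9 to 12 points at 25%, and 18 to 29 points at 50%. These figures assume that 2 or more events in the first 3 patients means unsafe, and that patients replaced for other reasons carry the same risk.

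Two stronger readings are not supported. A reader might infer that all severe events before light are dropped; an event on Day -2 or Day -1 in a patient who still receives I-PDT is counted. A reader might also infer that the response rate is biased by the same replacement rule; 12.1.3 states no response denominator, and an analysis restricted to patients who received I-PDT is a design choice in a single-arm study, not an error.

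**What to change.** In 12.1.9, state that:

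1. the lead-in set is every Cohort B patient who starts the study regimen, meaning palliative radiotherapy or porfimer sodium;
2. a patient with a related grade 4 or higher event counts in the lead-in, even if replaced for efficacy under 4.1.4;
3. a patient who misses I-PDT without such an event may still be replaced.

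Add a cross-reference in 4.1.4. This changes who is counted and no element of treatment.

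The work is a few sentences. The real cost is that the lead-in will expand to six, or declare the regimen unsafe, more often than under the current wording. For example, at a true rate of 20% and a 25% share, the chance of not being declared safe after three patients rises from 1 − 0.842³ = 0.403 to 1 − 0.8³ = 0.488, and P(unsafe) rises from 0.202 to 0.291. That restores the performance the rule has when every event is counted; it does not make the rule stricter than its own thresholds.

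A supportive response rate that counts non-illuminated patients as non-responders is optional and not needed to close this point.

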6.1.10 Risks and Benefits

This is a Greater Than Minimal Risk study according to IRB criteria. Phototoxicity is the most likely potential risk associated with the systemic administration of the porfimer sodium. Proper shielding from the operating room lights will be maintained and the pulse oximetry sensor will be rotated every 20 - 30 minutes to minimize this risk. The subjects will be provided with written instructions on how to protect themselves from excessive light exposure.

The site-specific toxicity associated with this therapy includes:

- Injection site reaction: Very common effects include pain at the injection site (12%) which is transient and can be minimized by slowing the injection rate. Common effects include injection site reaction (3%) and burning sensation (3%).
- Tumor/local tissue reaction: Very common effects include pain (15%), hemorrhage (15%) and scarring (12%). Common effects include edema (8%), localized infection (8%), fever (8%), and skin necrosis (2%).
- Phototoxicity: Common effects include sunburn (3%), blisters (5%), erythema (5%), hyper-pigmentation (3%), and cutaneous photosensitivity (3%).
- Other systemic events: Constipation (11%), vomiting (9%), anemia (8%), nausea (6%), and giddiness (2%).

Potential Procedural Risks of EBUS-TBN Guided I-PDT and/or I-PDT and/or PDT

- Bronchial bleeding from the insertion site
- Extension of the bronchoscopic procedure duration
- Minimal risk of pneumothorax, infection, mediastinitis, allergic reaction to porfimer sodium
- Airway perforation

Standard of care palliative radiotherapy followed by I-PDT. It is not known what the risk is for administering the I-PDT two days after standard of care palliative radiotherapy.

Potential Benefits of the Proposed Research

For participants that have partial or complete response to I-PDT and/or PDT, the potential benefits include a significant reduction in tumor mass and symptoms. There is no guarantee of the outcome, nor is it possible to predict whether or not any specific participant will respond to porfimer sodium I-PDT and/or PDT.

The data that will be collected in this study will allow the research team to evaluate the safety and provide indication on the potential efficacy of this treatment. If shown to be safe, we will use this data to design Phase I/II studies to confirm safety and test the efficacy of EBUS-TBN guided I-PDT with porfimer sodium.

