11 DATA AND SAFETY MONITORING

The Roswell Park Data and Safety Monitoring Committee (DSMC) will assess the progress of the study, the safety data, and critical efficacy endpoints. The DSMC will review the study annually and will make recommendations that include but not limited to; (a) continuation of the study, (b) modifications to the design, (c) suspension of or, (d) termination of the study.

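### Cohort B has no numerical toxicity boundary after its 3-to-6-patient lead-in, and a true 30% or 40% rate of related grade 4 or higher events passes that lead-in with probability 0.49 or 0.31

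*Combined protocol and SAP*

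**What the plan says.** All references are to the combined protocol and SAP.

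- **Event counted (12.1.9).** A treatment-related adverse event of at least "grade 4 with attribution of 'possible', 'probable', or 'definite', according to the NCI CTCAE v5.0".
- **Rule (12.1.9).** For none in three, and for one in six after expansion: "grade 4's are observed it will be concluded the therapy is safe". For one in three: "grade 4's are observed, enroll 3 more patients for safety evaluation". For two or more in six: "grade 4's are observed it will be concluded that therapy is unsafe". Two or three events in the first three patients are not written out.
- **Operating characteristics (12.1.9).** The plan prints, for a true "grade 4 rate is 20%, 30% and 40% the respective probabilities of declaring the treatment unsafe are 0.26, 0.51 and 0.70".
- **Cohort size (12.1.6).** 39, including 6 from the Phase I part.
- **Later interim look (12.1.7).** "A futility analysis of efficacy will be carried out for Cohort B after n=20 subjects have completed the trial". It uses conditional power, with no stated threshold, and does not look at toxicity.
- **Other safety provisions.** Section 12.1.8 is descriptive. Section 11 says "The DSMC will review the study annually" and lets the committee recommend modification, suspension or termination. Section 15.1.2 allows termination at any time for safety. None of these carries a number.
- **Prior knowledge (6.1.10).** "It is not known what the risk is for administering the I-PDT two days after standard of care palliative radiotherapy".

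**The concern.** The lead-in ends in a conclusion of safety, and the remaining 33 to 36 of 39 patients are treated without a pre-stated toxicity criterion. Three to six patients cannot support that conclusion for a combination whose risk the protocol calls unknown. Section 4.1 has Cohort 0 supply the safety component for Cohort A, which does not receive radiotherapy, so Cohort 0 does not fill the gap. Section 4.1.4 allows up to 32 patients from external sites and up to 10 years of accrual, so events may be scattered across centres and time. A pooled count with agreed triggers is most useful in that setting.

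**Working it through.** **Inputs.** The lead-in rule and printed probabilities (12.1.9), n = 39 (12.1.6), and the 0.20 limit that 12.1.2 sets for Cohort 0. Two assumptions: 2/3 and 3/3 count as unsafe, since they already meet two or more of six, and an unsafe finding ends Cohort B accrual.

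**1. Reproducing the plan's figures.** With true rate p:

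P(pass) = (1−p)³ + 3p(1−p)² × (1−p)³, and P(unsafe) = 1 − P(pass).

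| p | P(0/3) | P(1/3, then 0/3) | P(pass) | P(unsafe), exact | Plan prints |
|---|---|---|---|---|---|
| 0.20 | 0.512 | 0.384 × 0.512 = 0.197 | 0.709 | 0.291 | 0.26 |
| 0.30 | 0.343 | 0.441 × 0.343 = 0.151 | 0.494 | 0.506 | 0.51 |
| 0.40 | 0.216 | 0.432 × 0.216 = 0.093 | 0.309 | 0.691 | 0.70 |

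The 30% and 40% figures reproduce. The 20% figure does not: a 200,000-run simulation gives 0.293. Other readings of the rule give 0.345 (a fixed two or more of six), 0.283 (leaving out 3/3), 0.187 (expansion path only) and 0.095 (three or more of six). Even allowing for rounding (0.265), simulation error explains it only with about 4 × 0.2914 × 0.7086 / (0.2914 − 0.265)² ≈ 1,200 runs or fewer.

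**2. What a pass shows.** One-sided 95% exact upper limits on the rate are 1 − 0.05^(1/3) = 63% after 0/3, and 58% after 1/6 (95th percentile of Beta(2, 5)).

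**3. Expected patients with an event if all 39 are treated after a pass.** This is 36p after 0/3 and 1 + 33p after 1/6, weighted by the two routes in the table.

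- 30%: 10.8 and 10.9, so about 11.
- 40%: 14.4 and 14.2, so about 14.

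**4. An example boundary added to the lead-in.** With a Beta(1,4) prior and x events in n patients, the posterior is Beta(1 + x, 4 + n − x). Pause when P(rate > 0.20) is at least 0.90. At n = 10, four events give 0.870 and five give 0.956, so the trigger is 5/10. The same step gives 6/15, 7/20, 9/25, 10/30 and 11/35. Exact recursion over n = 1 to 39, keeping the lead-in, gives:

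| True rate | P(flag), lead-in only | P(flag), with boundary | Mean treated, lead-in only | Mean treated, with boundary |
|---|---|---|---|---|
| 0.10 | 0.094 | 0.095 | – | – |
| 0.20 | 0.29 | 0.34 | – | – |
| 0.30 | 0.506 | 0.716 | 21.7 | 18.4 |
| 0.40 | 0.691 | 0.946 | 15.2 | 10.6 |

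The means treat a flag as the end of accrual and leave out every other route to stopping. For the lead-in alone at 40%: 3 × 0.352 + 6 × 0.339 + 39 × 0.309 ≈ 15.2.

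**The case against.** The best defence is that oversight continues and that the sponsor disclosed the lead-in's limited detection. Both are true. Serious events reach the coordinating site within 24 hours (10.1.5), unexpected related ones are reported as Unanticipated Problems and go on to the IRB (10.1.5, 10.1.7), the DSMC can recommend suspension (section 11), and the study can be terminated for safety (15.1.2). If Cohort B took 5 to 10 years to accrue (an assumption), annual review would fall about every 39/10 to 39/5, or 4 to 8, patients, close to the looks proposed here. Faster accrual would weaken that. What stands against the defence is that none of these routes says what count should prompt action.

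A reader might infer several stronger things that the documents do not support:

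- **That 31–49% is the chance of treating all 39.** It is the chance of passing the lead-in. The futility look or the oversight above could stop accrual first. As an illustration, assume stopping when conditional power under a 50% response rate is below 10% or 20%, with success at 17/39 or more. The look then stops 24% or 42% of the time if the true response rate is 30%, but only 0.6% or 2% if it is 50%.
- **That later events have no consequence.** The reporting and termination routes contradict this. Only the numerical rule ends.
- **That about 12 or 16 events follow a pass.** Those are 39 × 0.30 and 39 × 0.40, which ignore that a pass means at most one event in the lead-in.
- **That the plan sets 0.20 as Cohort B's limit.** Section 12.1.2 sets it for Cohort 0. Section 12.1.9 uses 20%, 30% and 40% only as scenarios.
- **That the combination had never been given to a patient, or that all severe events count.** Section 1.1.10 reports one compassionate-care patient, and grade 3 events are outside the rule.

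**Conclusion.** The point holds as a weakness of design. It is neither a contradiction nor an absence of safety oversight. Cohort B has no numerical toxicity boundary after its first 3 to 6 patients, and the lead-in misses a 30% rate about half the time (0.49) and a 40% rate about three times in ten (0.31). The plan's own 0.51 and 0.70 imply nearly the same. This rests on reading 2/3 and 3/3 as unsafe and on independent events at a constant rate. The benefit of the added boundary also depends on the chosen limit, prior, cutoff and looks, which are illustrative. The change is worth making, because the combination's risk is declared unknown and the data needed are already collected. Separately, the printed 0.26 at a 20% rate should be 0.29.

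**What to change.** 1. Keep the lead-in and write out that 2/3 and 3/3 count as unsafe, if that is intended.
2. Continue the same count, related grade 4 or higher, in every treated Cohort B patient. Pause accrual for DSMC review when the posterior probability that the rate exceeds a stated limit is at least 0.90.
3. State the limit for Cohort B. One option is to carry over the 0.20 of 12.1.2, which the sponsor would have to confirm. With that limit and a Beta(1,4) prior, the triggers are at least 5/10, 6/15, 7/20, 9/25, 10/30 and 11/35.
4. Put the operating characteristics in 12.1.9, replace 0.26 with 0.29 for the lead-in, and cross-refer from section 11.

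**Cost.** Wording in the plan and the DSMC's instructions, with no extra patients or assessments. The chance of a flag rises from 0.29 to 0.34 at a true 20% rate and barely moves at 10% (0.094 to 0.095). A flag after the lead-in is a pause for review, so a false one costs time and does not by itself end the cohort. Related grade 4 or higher events must also be counted promptly: the 24-hour route covers serious events, while routine reporting in 10.1.3 sets no comparable deadline for non-serious ones.
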